It is recognized that at the time of the first onset of symptomatic HF event some patients may discontinue randomized treatment and may be prescribed an alternative treatment for HF which could be locally available Entresto™ (sacubitril/valsartan, LCZ696). For endpoints (1), (3), (4) and (5), the secondary analysis described above will estimate the treatment effect of LCZ696 vs ramipril including any effect of prescribed Entresto™ for ramipril patients who discontinued study drug and took Entresto™ as an alternative treatment. Hence, the following supportive analyses aim to estimate the pure treatment effect as though in a situation whereby Entresto™ was not an available treatment option for HFrEF.

Endpoints (1), (3) and (5) will be analyzed using an inverse probability of censoring weighted (IPCW) Cox proportional hazards model (Robins and Finkelstein 2000). In this analysis, the censoring mechanism will be the same as described for the primary analysis for patients who are not prescribed Entresto™. For patients who do, censoring will occur at the minimum of the last date the endpoint status was known, the time of death from non-CV causes or 28 days after study treatment discontinuation. To adjust for the potential informative censoring, patients with event times censored due to treatment switch will be dynamically replaced in the patient risk-set to be represented by patients in control arm with a matching prognostic profile by up-weighting such patients in the analysis set. The weights will be calculated using a logistic regression with clinical risk factors determinant of developing the endpoint as covariates in the model (both baseline and post-baseline). A weighted Cox proportional hazard model will be fitted to this modified risk set. The model will be stratified by STEMI/NSTEMI; region, PCI use at baseline will be included as covariates. The hazard ratio for LCZ696 vs. ramipril, the associated 2-sided 95% confidence interval and the 1-sided and 2-sided p-values will be presented from the analysis. Further details on appropriate covariate adjustment and associated implementation will be prospectively provided in the statistical analysis plan.

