2.6.5 Supportive analysis and sensitivity analysis

Supportive analysis

It is recognized that at the time of the first onset of symptomatic HF event some patients may discontinue randomized treatment and may be prescribed an alternative treatment for HF which could be locally available Entresto™ (sacubitril/valsartan, LCZ696). For the pre-specified secondary endpoints (1), (3) and (5) (numbering refers to Section 2.6.1), the analysis described in [Section 2.6.2](#) will estimate the treatment effect of LCZ696 vs ramipril including any effect of prescribed Entresto™ for ramipril patients who discontinued study drug and took Entresto™ as an alternative treatment. Hence, the following supportive analyses aim to estimate the pure treatment effect as though in a situation whereby Entresto™ was not an available treatment option for HFrEF. In this regard, as a sensitivity analysis, inverse probability of censoring weighted (IPCW) Cox proportional hazards model ([Robins and Finkelstein 2000](#)) will be performed on the secondary endpoints (1), (3) and (5).

Inverse probability of censoring weighted (IPCW) Cox proportional hazards model

In the IPCW analysis, the following censoring mechanism will be used for the event generating process for secondary endpoints:

- For patients randomized to LCZ696 and patients randomized to ramipril but did not take open label Entresto upon diagnosis of HFrEF event will be censored according to the mechanism described for the secondary endpoints.
- For patients randomized to ramipril who subsequently start taking open label Entresto, (defined as treatment switch), censoring will occur at the minimum of the last date the endpoint status was known, the time of death from non-CV causes, 28 days after study treatment discontinuation or start of open-label Entresto.

To adjust for the potential informative censoring, patients in the ramipril arm with event times censored due to treatment switch will be dynamically replaced in the patient risk-set by remaining uncensored patients in the ramipril arm with a matching prognostic profile by up-weighting such patients in the analysis set. At a specific time, patients in the ramipril arm who have not switched to taking open label Entresto will be assigned a weight inversely proportional to the probability of not switching till that time (i.e., patients who do not switch, but have covariates implying a high probability of switching, get a larger weight in the analysis).

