Estimating IPC weights

In order to predict these patient specific time-varying probabilities, the time scale is split into small intervals based on the visit schedules. In each interval the conditional probability of being switched given patient has not switched at any earlier interval is modelled using a logistic regression model with the following covariates–

- **Time independent (baseline) covariates:**

Age (in years), baseline LVEF, baseline eGFR (ml/min/1.73m²), history of prior MI (yes/no), history of diabetes (yes/ no), Atrial Fibrillation associated with qualifying MI (yes/no), baseline Killip class, use of PCI for qualifying MI (yes/ no), use of ACEI/ARB in last 24 hours prior to randomization (yes/ no), use of IV treatment for qualifying MI (yes/ no)

- **Time dependent covariates:**

Systolic BP (mmHg), Heart rate (bpm), eGFR (ml/min/1.73m²), *use of PCI or CABG (yes/ no), *use of ICD/CRT (yes / no)

*(*procedures related to any post-randomization MI event)*

Predicted probability of switching at a specific time for a patient will be obtained by multiplying individual conditional probabilities of switching in intervals prior to that time point. To minimize impact of extreme weights (e.g. patients not switched though having very high estimated probability to switch), the stabilized version of weights will be used which is defined as the ratio of predicted probabilities of not being switched by time t –

- from the logistic regression with only baseline covariates
- from the logistic regression with both baseline and post-baseline covariates

It is conceivable that the above logistic regression procedure of estimating weights may not converge due to reasons including (but not limited to) sparseness of switchers in the subpopulations implied by the selected covariates resulting into an infinite likelihood due to complete or quasi-complete separation or numerical difficulties in evaluating an overly complex likelihood function. Should such problems arise, the logistic regression model used to determine the IPC weights will be simplified by pooling pre-specified time intervals (thereby extending the time windows in which time-dependent covariates are assessed). If that still does not solve convergence problems, the model will be simplified by removing covariates.

All patients randomized to LCZ696 will be assigned a weight of 1 for all time intervals.

Estimation of treatment effect

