Following the estimation of weights, a weighted Cox proportional hazard model will be fitted to the time to event endpoints (1), (3) and (5). The model will be stratified by STEMI/NSTEMI while treatment, region, PCI use at baseline will be included as fixed effects factors. The hazard ratio for LCZ696 vs. ramipril, the associated 2-sided 95% confidence interval and the 1-sided and 2-sided p-values will be presented from the analysis.

On-treatment analysis

Endpoint (4), the total number of confirmed hospitalizations for HF, MI and stroke (including CV death) will be redefined for the patients who are prescribed open label Entresto™ as the

total number of composite endpoints from randomization up to 28 days after the time of study treatment discontinuation. The analysis methods will remain the same as specified above.

Sensitivity analysis

If the study is stopped early for efficacy at the second interim analysis, or the study is terminated early by the sponsor due to prolonged COVID-19 impact, a sensitivity analysis using the primary/main analysis model as specified in [Section 2.6.2](#) will be performed for each secondary endpoint, including all data accrued up to the end-of-study analysis cut-off.

If the study is not stopped at the second interim analysis and continues to the end, a sensitivity analysis using the primary/main analysis model as specified in [Section 2.6.2](#) will be performed for each secondary endpoint, including data accrued prior to 01-Mar-2020.

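### In the supportive open-label Entresto analyses, cutting follow-up 28 days after study drug stop only for patients who later start Entresto makes the cut depend on the future and can drop non-fatal events that precede the switch

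*SAP*

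**What the plan says.** SAP 2.6.5 defines the patients concerned as follows: "For patients randomized to ramipril who subsequently start taking open label Entresto, (defined as treatment switch". For them, "censoring will occur at the minimum of the last date the endpoint status was known, the time of death from non-CV causes", and then the two drug-related dates, "28 days after study treatment discontinuation or start of open-label Entresto". LCZ696 patients, and "patients randomized to ramipril but did not take open label Entresto upon diagnosis of HFrEF event", keep the ordinary censoring of the secondary endpoints.

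The inverse-probability weights come from a logistic model, by visit interval, for the "conditional probability of being switched given patient has not switched at any earlier interval".

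Protocol 9.5.1 has an earlier form of the rule. For any patient prescribed Entresto, in either arm, the dates end with "the time of death from non-CV causes or 28 days after study treatment discontinuation"; the start of Entresto is not among them.

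For endpoint (4), the total event count, SAP 2.6.5 redefines the outcome for patients prescribed Entresto as the "total number of composite endpoints from randomization up to 28 days after the time of study treatment discontinuation". This too has no arm restriction. The text says the methods are otherwise unchanged and does not say whether follow-up time ends at the same date.

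**The concern.** Whether a patient is a switcher is known only on the day Entresto starts. The rule nevertheless moves that patient's censoring back to 28 days after the stop whenever that date is earlier. Two ramipril patients with the same history up to that day are then handled differently because of what one of them does later.

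The time removed is time the patient lived through without Entresto, which is what the analysis is meant to observe. For endpoints with a non-fatal component, an event in that time is removed too: HF hospitalization in (1), MI or stroke in (3). For HF hospitalization this matters because the plan itself expects Entresto to be prescribed around symptomatic HF, so the lost event may be the reason for the switch. At stake is whether the reported hazard ratio, interval and p-values answer the question the analysis was written to answer.

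**Working it through.** **Which date governs.** Protocol 5.5.8 requires study drug to be stopped at least 36 hours before Entresto, so the stop comes first. The drug-related censoring date is min(stop + 28, Entresto start).

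- Stop day 100, Entresto day 110: min(128, 110) = 110. The 28-day limb has no effect.
- Stop day 100, HF hospitalization day 300, Entresto day 310: min(128, 310) = 128. The day-300 event is lost although no Entresto had been taken. Censoring at Entresto start keeps it.

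If the 28 days is read as attaching to both dates, the second case gives min(128, 338) = 128, the same answer. In the SAP rule the limb therefore acts only when the gap exceeds 28 days, and then only on pre-switch follow-up.

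**Can the gap be long?** No section caps it. Protocol 5.5.6 directs patients who stop for intolerable adverse effects to an open-label ACE inhibitor or ARB, and Protocol 5.6.2 keeps patients in follow-up after they stop, so events in the gap are collected.

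**Do the weights correct it?** The modelled outcome is the switch. The listed covariates include neither study drug discontinuation nor HF events. Nothing in the model describes censoring at stop + 28 days.

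**By endpoint.** A patient who dies cannot switch afterwards, so no death can be deleted. For (5), and for the CV death component of (1) and (3), the rule removes only event-free time. In the SAP analysis this raises the ramipril hazard and lowers the hazard ratio. Deleting non-fatal ramipril events does the reverse.

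**Yardstick.** The plan gives no figure for this rule. Its power for endpoint (1) in SAP 3.2 (592 events, HR 0.80, one-sided 2.5%) reproduces: |ln 0.80| × √592 / 2 − 1.960 = 2.715 − 1.960 = 0.755, and Φ(0.755) = 77.5%, as stated. The matching standard error of the log hazard ratio is 2/√592 = 0.082.

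**Illustrative size, endpoint (1).** Event rates are those of SAP Table 3-5 (6.0%, 7.5%, 9.6%, and 10.9% at 18 months). The following are assumptions: follow-up uniform over 4 to 41 months; 65% of events are HF hospitalizations; 3% per year background switching after the stop; event-triggered switching 7 days after the later of event and stop; true HR 1. The Cox model is unweighted, with 400,000 simulated patients per row. Event counts are scaled to 2,825 ramipril patients.

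| Stops per year | HF-hospitalized who switch | HR, SAP rule | HR, cut at Entresto start | Change | Ramipril events lost |
|---|---|---|---|---|---|
| 10% | 10% | 1.000 | 0.997 | +0.3% | 1.4 of 333 |
| 10% | 25% | 0.995 | 0.986 | +0.9% | 3.4 of 332 |
| 10% | 50% | 1.014 | 1.000 | +1.4% | 5.3 of 330 |
| 20% | 10% | 0.999 | 0.993 | +0.6% | 2.7 of 331 |
| 20% | 25% | 1.019 | 1.005 | +1.4% | 5.4 of 327 |
| 20% | 50% | 1.044 | 1.013 | +3.1% | 10.7 of 328 |

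Both hazard ratios in a row use the same simulated patients, so the change is the figure to read.

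A second simulation used true HR 0.80, the same event rates, 10% to 22% stops per year, 0% to 40% of HF events triggering Entresto, and 0% to 3% per month other switching. The ratio of the two hazard ratios ran from 0.992 (switching unrelated to events) to 1.024 (event-triggered), with up to 2.6% of ramipril events deleted.

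**Endpoint (5).** Assuming 5% per year mortality, 10% or 20% stops per year and 3% or 15% per year switching, the hazard ratio moved by -0.2% (0.988 against 0.990) to -1.9% (0.976 against 0.995). No deaths were lost.

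**Against the yardstick.** The largest shift is ln(1.031)/0.082 = 0.37 standard errors. It would take an HR of 0.80 to 0.80 × 1.031 = 0.825.

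**The case against.** The strongest reply is that the plan describes a different course: symptomatic HF, then stopping study drug, then Entresto, close together. The HF event then precedes stop + 28 days and is counted. That is right, and the rule is harmless there. A reader might infer that the plan's expected switcher loses the HF event; the text does not support that. The harm is confined to gaps over 28 days, whose frequency is unknown.

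A reader might also infer that the rule distorts one arm only. That holds for the SAP weighted analysis. Protocol 9.5.1 and the endpoint (4) rule cover Entresto users in either arm.

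For endpoint (4), SAP 2.6.5 calls the analysis on-treatment, and SAP 2.1.1 defines on-treatment data as ending 28 days after permanent discontinuation. This suggests that follow-up time should end there too, so the silence is partly answered. It does not explain why the cut falls only on patients later prescribed Entresto. The on-treatment analysis of the primary endpoint in SAP 2.5.4 applies to everyone who discontinues.

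Finally, the simulations apply no weights and use assumed inputs. That stands. The statement that weighting does not correct the rule rests on what the weights model, not on a weighted simulation.

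**Conclusion.** The concern holds as a defect in the supportive analyses. For gaps over 28 days the censoring date depends on later Entresto use, removes pre-switch time and non-fatal events, and falls on a date the weights do not model.

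The size is not known from the documents. Under the assumptions above it is roughly -1% to +3% on the endpoint (1) hazard ratio and about -0.2% to -1.9% for endpoint (5). The rule does not consistently favour either arm: losing non-fatal ramipril events works against LCZ696, while losing event-free ramipril time works in its favour.

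A reader might infer that the trial's confirmatory conclusions are at risk. They are not. These analyses are outside the hierarchy in SAP 2.6.3, and the primary analysis, the treatment-policy analyses in SAP 2.6.2 and the interim stopping rules do not use this cut. The change should still be made: the rule works against the purpose of the analysis, and the limb adds nothing when Entresto starts within 28 days of the stop.

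**What to change.** In SAP 2.6.5, delete the limb for 28 days after study treatment discontinuation. Switchers are then censored at the minimum of last known endpoint status, non-CV death and start of open-label Entresto. Align Protocol 9.5.1, including which arm or arms the rule covers.

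For endpoint (4), end both the event count and the follow-up time at the start of Entresto. If it is to remain an on-treatment analysis, apply the cut at stop + 28 days to all patients who discontinue, and end follow-up time at the same date.

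The cost is one clause in the SAP, a matching change in the protocol and a sentence for endpoint (4). No new data are needed: concomitant medication is recorded (Protocol 5.5.7), and SAP 2.4.1 already summarizes exposure to open-label Entresto.

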If a patient withdraws from participation in the study, refuses to return for study assessments or is unable to do so, every effort should be made to contact them or a knowledgeable informant by telephone and/or other measures to determine the patient's survival status and endpoint information including heart failure hospitalization or outpatient heart failure events during the follow-up period.

Patients eligible to participate in this study must be randomized between 12 hours to 7 days after index AMI event presentation.

Prospective study candidates will be identified either during the hospitalization for the index AMI or post discharge up to 7 days after the index MI presentation. After identifying a potential patient, an informed consent form (ICF) must be signed before performing study-related screening procedures that are not considered standard of care for AMI patients at that site. Procedures that are part of a site's standard of care for an individual with AMI may pre-date the signed ICF. The AE and SAE reporting period will begin at the time the ICF is signed. Screening will continue until the patient has been deemed eligible for randomization into the study up to 7 days after the index MI. Screening and randomization can occur on the same day.

Visit 101 will be considered the reference visit for all study visits during the treatment epoch. Regardless of the occurrence of any unscheduled visits, scheduled visits should be performed within the specified timeframe in relation to Visit 101 as outlined in [Table 6-1](#). If a visit is completed earlier than scheduled or postponed, it should not result in the next visit being brought forward or postponed.

Visits are planned to occur at weeks 1, 2, 4 (month 1), month 2, month 4, and then every 4 months until study end.

Epoch	Screen	Treatment																		
Visit	1	101	102	103	104 ¹⁶	105	106	107	108	109	110	111	112	113	114	115 ¹⁷	116 ¹⁷	117 ¹⁷	199 and PSD	
Day		1	7	14	28	61	122	243	365	486	608	730	851	973	1095	1216	1338	1460	EOS	
Week		0	1	2	4	8	17	34	52	69	86	104	121	138	156	173	190	208	EOS	
Month					1	2	4	8	12	16	20	24	28	32	36	40	44	48	EOS	
Serum/urine pregnancy testing ^{2,11}	S	S							S			S			S			S	S	
Dispense Study Medication		X	X	X	X	X	X	X	X	X	X	X	X	X	X	X	X	X	X	
Contact IRT	X	X	X	X	X	X	X	X	X	X	X	X	X	X	X	X	X	X	X	X
Screening disposition	X																			
Study Completion form																				X

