6.4.3 Appropriateness of efficacy assessments

The composite of CV death or HF hospitalization is a well-established mortality and morbidity endpoint. The addition of the outpatient HF component here aims to capture the clinically important outpatient symptomatic HF event that contributes to the totality of HF morbidity following an AMI presenting as either inpatient (i.e., HF hospitalization) or outpatient (i.e., outpatient HF) events. The clinical significance of HF events in the outpatient setting has been increasingly recognized by medical communities and health authorities ([Hicks, et al 2014](#)). Outpatient HF events reported in randomized chronic HF trials, of which the definition is analogous to the outpatient HF event proposed for CLCZ696G2301 study, have been shown to be associated with significantly increased risks of (CV) mortality. Furthermore, the outpatient HF events are also modifiable events that are equally sensitive to the evidence-based HF therapeutics as are the mortality and composite CV death/HF hospitalization endpoints, which underscores the similar pathology contributing to these events ([Skali, et al 2014](#); [Okumura, et al 2016](#)).

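### The weights for the open-label Entresto analysis leave out post-randomization heart failure, which the plan itself names as the occasion for switching

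*SAP*

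**What the plan says.** Protocol Section 9.5.1 and SAP Section 2.6.5 give the same reason for the analysis: "at the time of the first onset of symptomatic HF event some patients may discontinue randomized treatment" and may then be prescribed open-label Entresto. The protocol wants the weights built from "clinical risk factors determinant of developing the endpoint as covariates in the model (both baseline and post-baseline", and leaves the detail to the SAP. The SAP says switchers will be represented by "remaining uncensored patients in the ramipril arm with a matching prognostic profile".

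The SAP's time-dependent list starts "Systolic BP (mmHg), Heart rate (bpm), eGFR" and ends with PCI or CABG and ICD or CRT, both restricted to procedures for a post-randomization MI. No HF hospitalization, outpatient HF or loop diuretic term appears, and no other readable section adds one.

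The weight model works by visit interval: "the time scale is split into small intervals based on the visit schedules". Protocol Section 6 places visits at weeks 1, 2 and 4, month 2, "month 4, and then every 4 months until study end". If the logistic model does not converge, intervals are pooled first and covariates are then dropped, in no stated order. Only ramipril patients are censored for switching. Every LCZ696 weight is 1.

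**The concern.** Weighting removes informative censoring only if the common causes of censoring and outcome are in the weight model. The documents name HF onset as a cause of censoring. As for outcome, Protocol Section 6.4.3 says of "Outpatient HF events reported in randomized chronic HF trials" that they "have been shown to be associated with significantly increased risks of (CV) mortality". A prior HF event is therefore the leading candidate for a time-varying confounder, and it is absent.

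The error falls on one arm. Ramipril patients who have had HF leave the risk set when they switch, and weights blind to HF rebuild that risk set mostly from patients without HF.

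- For (3) and (5), neither kind of HF event ends time at risk, so the problem applies in full.
- For (1), HF hospitalization is itself an endpoint event, so only outpatient HF matters and the effect is small.

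Baseline covariates give little protection, because they enter both numerator and denominator of the stabilized weight and largely cancel. At stake is whether a reported HR, confidence interval and p-value estimate what the SAP says they estimate.

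**Working it through.** **Yardstick.** SAP Table 3-6 gives endpoint (3) 594 events, a 15% risk reduction and 50.8% power at one-sided 2.5%. The standard error of log HR is 2/√594 = 0.0821. Then |ln 0.85|/0.0821 = 0.1625/0.0821 = 1.981, less 1.960 leaves 0.021, and Φ(0.021) = 0.508. The stated power is reproduced, so 0.082 is a fair unit.

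**Inputs from SAP Section 3.2.**
- Pooled HF rates 5.4, 6.6, 8.3 and 10.3%, and endpoint (3) rates 4.6, 6.0, 8.7 and 11.0%, at 3, 6, 12 and 18 months.
- Accrual of 463 patients by month 10, about 2,400 by month 24, then 250 a month to month 37; cut-off at month 41; 0.5% a year lost.
- Piecewise hazard = −ln[(1−F₂)/(1−F₁)]/(t₂−t₁). For HF in months 0–3 this is −ln(0.946)/3 = 0.0185 per month.

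**Assumptions not in the documents.** A share p of ramipril HF patients switches (10–50%) after a mean delay of 1 week to 3 months. Hazard after HF is multiplied by k (2 to 6). The listed covariates carry no information on HF.

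**Mechanism by hand.** Let f be the share with prior HF. The true mean ramipril hazard is proportional to 1 − f + kf. After switchers are removed and HF-blind weights applied, it is [1 − f + kf(1−p)]/(1 − fp). Take k = 4 and p = 0.25, ignoring switching delay and depletion:
- Month 3, f = 0.054: 1.162 ÷ [(0.946 + 0.162)/0.9865] = 1.162/1.123 = 1.035.
- Month 12, f = 0.083: 1.249 ÷ [(0.917 + 0.249)/0.9793] = 1.249/1.191 = 1.049.

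The ratio is 1 at randomization, many events are early and switching is delayed, so the average is lower.

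**Full calculation, endpoint (3).** A day-by-day cohort with the HR solved from the Cox score gives, with no true effect and a one-month delay, 1.027 in this middle case; ln 1.027/0.0821 = 0.32 standard errors. Across the assumed range the excess runs from 0.3% (0.04 standard errors) to 8.9%. A second version of the calculation puts the top at 9.7%, or ln 1.097/0.0821 = 1.1 standard errors.

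With a true benefit (HR 0.85 within HF state, 0.83 for HF onset, 0.85 for Entresto after switching):

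| Switching, hazard after HF | Target HR | Intention-to-treat HR | IPCW as written |
|---|---|---|---|
| 10%, 4-fold | 0.833 | 0.834 | 0.842 |
| 25%, 4-fold | 0.833 | 0.837 | 0.856 |
| 25%, 2-fold | 0.843 | 0.846 | 0.852 |

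In each row the weighted analysis lies further from its target than the unadjusted one.

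**If only CV death is raised.** CV death without prior HF is approximated by the primary composite minus the HF composite: 7.2−5.4, 8.6−6.6, 11.0−8.3 and 13.0−10.3, that is 1.8, 2.0, 2.7 and 2.7%. Its share of the (3) hazard is 39% in months 0–3, 13.8% in months 3–6 and 13.1% in months 6–18 pooled. The middle case for (3) is then 0.6% (0.07 standard errors), with a range of 0.1–1.9%. For (5), counting CV deaths only (about 157–183, standard error 0.15–0.16), it is 2.2% (0.14 standard errors), range 0.3–7.1%. For (1) it is 0.6% (0.07 standard errors).

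**Testing the remedy, middle case for (3), no true effect.** The HR is 1.027 with no HF term, 1.017 with HF status at interval start and 1.004 with the interval split at the HF date. A patient-level simulation (600 runs, 2,825 per arm) gives 1.028, 1.018 and 1.005 (Monte Carlo standard error 0.003). At 50% switching it gives 1.061, 1.037 and 1.008.

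**The case against.** The strongest reply is about importance. The analysis is supportive and outside the testing hierarchy. The only prognostic statement in the documents concerns CV mortality after outpatient HF in chronic HF trials, and on that basis the middle case for (3) is 0.07 standard errors. The larger figures also need raised MI and stroke hazards, which no section asserts. Protocol Section 5.5.6 recommends an ACE inhibitor or ARB after intolerance, which argues against heavy switching. All of this stands, and it limits the size.

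Three technical points also stand in part.
- The bias is upward; it is toward 1 only if LCZ696 is beneficial. Its direction also assumes that HF patients who switch carry the same raised risk as those who do not.
- Blood pressure, heart rate and eGFR may track HF. Read at interval start they help little: a combined score shifted by 1 or 2 SD after HF leaves 1.026 or 1.024, and perfect tracking leaves 1.017. The SAP does not fix when they are read, and reading within the interval could do better.
- The CV-death subtraction is crude: it implies no such deaths in months 12–18, so those months must be pooled with months 6–12.

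The argument that the protocol merely deferred the choice of covariates does not answer the point. It asked for post-baseline determinants of the endpoint, and the SAP's closed list omits the event the plan itself ties to switching.

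**Conclusion.** The concern holds. Followed as written, the weights cannot correct for the stated occasion of switching, and the HRs for (3) and (5) are pushed upward. That the term is missing is certain. How much it matters is not, because switching frequency and post-HF risk are assumed: the middle case for (3) is 0.6% if only CV death is raised and 2.7% if the whole endpoint is. With few switchers, or covariates that track HF closely, it would be smaller. Under these assumptions the bias runs against LCZ696. The primary and main secondary analyses and the error rate are untouched. It should be corrected because the analysis otherwise misses its own purpose and can land further from its target than no adjustment.

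**What to change.** Before database lock, amend SAP Section 2.6.5 as follows.

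- Add to the denominator model a time-dependent indicator of prior HF hospitalization or outpatient HF for (3) and (5), and of prior outpatient HF for (1). Use investigator-reported as well as adjudicated events; SAP Section 2.5.4 already analyses both.
- Split each patient's visit interval at the HF date, or use an equivalent rule that orders HF before the switch. Status at interval start removes only 17–50% of the bias, depending on the delay.
- State the simplification order: drop other covariates before this term and before pooling intervals. With yearly windows even the split leaves 1.018.
- If nobody switches without prior HF, set that switching probability to 0 and keep the term.

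The cost is SAP wording and slightly more variable weights: the SD of log HR is unchanged at 0.081 with 25% switching and rises from 0.0886 to 0.0895 with 50%. That check did not fit the full covariate list, and separation is possible where few patients switch without HF.

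Some bias remains. The split removes about 76% or more in the cases run with a delay of 1 to 3 months, and slightly over-corrects (0.996–0.998) at 50% switching with a one-week delay. It does not help a patient who stops study drug, is censored 28 days later, and only then has HF and starts Entresto. HF managed by moving to Entresto without qualifying treatment is not captured as a confirmed event.
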